11	WITHDRAWAL OF PATIENTS OR PREMATURE TERMINATION OF THE STUDY	18
	11.1 Withdrawal of individual patients from protocol treatment	18
12	SAFETY	19
	12.1 Reporting of adverse events.	19
	12.2 Study Report	19
13	ENDPOINTS	19
	13.1 Primary endpoint.....	19

13.2	Secondary endpoints	19
14	STATISTICAL CONSIDERATIONS	20
14.1	Patient numbers and power considerations	20
14.2	Statistical analysis	20
14.3	Statistical analysis	20
15	TRIAL CONDUCT AND REGISTRATION.....	21
15.1	Trial conduct.....	21
15.2	Regulatory Documentation.....	21
15.3	Registration	22
16	DATA COLLECTION AND QUALITY ASSURANCE	22
16.1	Data quality assurance.....	22
17	ETHICS	23
17.1	Accredited ethics committee	23
17.2	Ethical conduct of the study	23
17.3	Patient information and consent	23
17.4	Trial insurance.....	24
18	ADMINISTRATIVE ASPECTS AND PUBLICATION	24
18.1	Handling and storage of data and documents	24
18.1.1	Patient confidentiality	24
18.1.2	Filing of essential documents	24
18.1.3	Record retention	24
18.2	End of study report.....	25
18.3	Publication policy	25
19	REFERENCES	26
	THIS PAGE INTENTIONALLY LEFT BLANK.....	27
	ANNEX 1	28
	ANNEX 2	29

2 Protocol Summary

Study title

A multicenter observational Belgian study assessing the impact of newly started treatments on the QOL in patients suffering from myelodysplastic syndromes.

Background

A disease specific Quality of life (QOL) assessment gives a view on disease-related symptoms and psychological sequelae of patients suffering from a MDS(MDS). This QOL assessment tool, the QUALMS (Annex 1), was developed by Abel and colleagues at Dana-Farber institute and validated afterwards (1).

Another important aspect is the patients' perception of the disease. This can be measured using the brief illness perception questionnaire (B-IPQ)(Annex 2) (2).

Study type

An observational study conducted in different hematological centers in Belgium.

Study objectives

Primary objective:

To assess the impact of newly started treatments on the QOL of patients suffering from myelodysplastic syndromes.

Secondary objectives:

- To assess the impact of newly started therapy on disease perception in MDS patients
- To study the relation between disease perception and quality of life
- To examine which clinical and disease specific factors determine QOL in MDS patients
- Collect information on the transfusion threshold in Belgian hematological centers and evaluate the impact on quality of life.
- To evaluate whether changes in QOL are related to hematological responses.

Study design

- Newly diagnosed MDS patients who are about to start a treatment or previously diagnosed MDS patients who are starting with a new line of therapy.
- QOL assessment with the QUALMS.
- Disease perception measurement using the B-IPQ.
- Measurement at diagnosis/before start of therapy, at 4 weeks, 12 weeks, and at 24 weeks into treatment.

Study endpoints*Primary endpoint:*

Change in QUALMS score at visit timepoints 4 – 12 – 24 weeks after the start of a new treatment.

Secondary endpoint:

- Change in B-IPQ score at visit timepoints 4 – 12 – 24 weeks after the start of a new treatment
- Association between B-IPQ and QUALMS score.
- Association between clinical and disease specific factors and QUALMS score
- Association between transfusion threshold and QUALMS score.
- Association between hematological response and QUALMS score

Summary of eligibility criteria

- Adult patients with a new diagnosis of MDS (according to WHO 2016 definitions (3) or known patients with MDS who are about to start a new treatment.
- Signed informed consent.
- Patients enrolled in an unblinded interventional therapeutic trial are eligible.

Exclusion criteria

- Patients with acute leukemia defined as >20% bone marrow blasts.
- Patients suffering from an overlap syndrome myelodysplastic/myeloproliferative disease.
- Patients in post allogeneic transplant setting.
- Patients enrolled in a blinded interventional therapeutic trial.
- Patients starting with multiple treatments under investigation at the same moment apart from intensive chemotherapy.
- Newly diagnosed patients who do not start with treatment.
- Patients who started a previous treatment less than 12 weeks ago apart from packed cell transfusion (up to 4 weeks allowed).
- Diagnosis of any previous or concomitant malignancy except when the patient successfully completed treatment (chemotherapy and/or surgery and/or radiotherapy) with curative intent for this malignancy at least 3 months prior to inclusion.
- Patients refusing to sign informed consent.

3 Investigators and study administrative structure

This is an investigator-initiated trial sponsored by UZA, which means that UZA holds all sponsor responsibilities unless it is explicitly stated in this protocol that a sponsor responsibility is delegated to another party.

Responsibility	Name	Affiliation/Address
Sponsor	UZA	
Principal Investigator	[name]	UZA

4.1 Myelodysplastic syndromes

Myelodysplastic syndromes refer to a heterogeneous group of clonal bone marrow disorders. They are characterized by malfunctioning of the bone marrow due to stem cells with aberrant morphology and maturation (dysmyelopoiesis). This is caused by cytogenetic abnormalities and molecular mutations. Bone marrow malfunctioning leads to one or more cytopenias in peripheral blood. Patients, most commonly in the aging population, frequently present with fatigue but recurrent infections or easy bleeding may occur in relation to the cytopenias that are found (4).

Depending on the findings in the bonemarrow and the genetic signature of the disease, patients are categorized in different risk groups to determine the risk for evolution to acute leukemia. The best implemented scoring system is the IPSS (International prognostic scoring system), assigning patients to the low, intermediate-1, intermediate-2 or high-risk category. The majority of patients present with lower-risk disease (low and intermediate-1) and have a survival of many years with supportive therapy only. Higher (intermediate-2 and high)-risk patients however demand more close attention and specific therapy to prevent evolution to acute leukemia. So far, the only curative option is allogeneic stem cell transplantation. Most patients however are not eligible for this intensive treatment (5). Apart from clinical trials, treatment options for this extensive group are limited. In lower risk diseases only supportive treatments can be offered with the exception of Del5q-syndrome in which lenalidomide is available. Only for higher risk patients, Vidaza® is reimbursed (6). Patients in need for treatment visit the hospital in a frequency that there therapy demands. Visits range between 15 minutes and whole day admissions depending on the treatment.

4.2 QOL assessment

Oxford dictionary defines the QOL as 'the standard of health, comfort and happiness experienced by an individual or group.' A broad range of life domains can influence this QOL so it is important to have attention for all of them when assessing quality of life. By assessing the quality of life, we can understand the general well-being of an individual or group. Based on this assessment, decisions can be made in general life, in a company but also in healthcare.

4.3 QOL assessment in MDS

To assess the QOL in the general population, different tools were developed in the past. Mostly they consist of questionnaires that try to cover all relevant topics that might have an influence on the quality of life.

If a subgroup of the population is approached, different topics become more relevant. For example, living above a supermarket at the age of 75 can have a totally different impact on QOL than at a younger age and working night shifts.

Fatigue as a result of anemia is the most frequent symptom of myelodysplastic syndromes. Assessment of QOL in the MDS population focused on this in the past. The FACT (functional assessment of cancer therapy) questionnaires for anemia (FACT-AN) and fatigue (FACT-Fatigue) were used to evaluate the efficacy of ESA (7). Higher risk diseases have been approached with focus on the malign aspect of the disease, using the EORTC C30 (8). However, since those assessments do not necessarily cover the subtleties of the disease, a specific questionnaire was developed. The use of this questionnaire gives us a specific assessment for disease-related symptoms and psychological sequelae of MDS patients (1). This specific questionnaire, the QUALMS will be used in this study to evaluate the QOL of patients suffering from MDS.

5 Study objectives

With growing sense of self-determination in Belgium, QOL becomes more relevant than it used to be. With this study, we aim to:

Primary objective:

assess the impact of newly started treatments on the QOL of patients suffering from myelodysplastic syndromes.

Secondary objectives:

- assess the impact of newly started therapy on disease perception in MDS patients.
- study the relation between disease perception and quality of life
- examine which clinical and disease specific factors determine QOL in MDS patients
- collect information on the transfusion threshold in Belgian hematological centers and evaluate the impact on quality of life.
- evaluate whether changes in QOL are related to hematological responses.

This study will not mutually compare the effect that different treatments have on QoL since the studied treatments will be installed at different stages of the disease and have different indications.

6 Study design

This study is an observational study conducted in different hematological centers in Belgium. The study will be conducted within the 'MDS Working Group' of the 'Belgian Hematological Society'. This working group is attended by members of different academic and non-academic hematological centers. Centers who are not represented in the working group will be approached only if follow up of MDS patients is done by a certified hematologist.

The QOL of will be measured in patients who are newly diagnosed with MDS or known patients that are about to start a new therapy. Patients that do not start with a treatment can not participate. All treatment discisions are made by the treating haematologist, this study will not interfere with this discions at any timepoint.

7 Study population

7.1 Eligibility for registration

All eligible patients must be registered before start of treatment and must meet all of the following eligibility criteria which will be checked at registration.

7.1.1 Inclusion criteria

- Newly diagnosed patients with myelodysplastic syndromes defined by WHO 2016 criteria that are about to start treatment.
- Patients with a known diagnosis of MDS, irrespective of IPSS and irrespective of time of diagnosis that are about to start a new therapy.
- Signed informed consent

7.1.2 Exclusion criteria

- Patients with acute leukemia defined as >20% bone marrow blasts.
- Patients suffering from a myelodysplastic/myeloproliferative overlap syndrome. In this case the disease has both dysplastic and proliferative features but cannot be properly categorized to either group. This category includes chronic myelomonocytic leukemia (CMML), juvenile myelomonocytic leukemia (JMML), atypical chronic myeloid leukemia (aCML) and myelodysplastic/myeloproliferative disease unclassifiable.
- Patients in post allogeneic transplant setting.
- Patients enrolled in a blinded interventional therapeutic trial.
- Patients starting with multiple MDS treatments at the same moment apart from intensive chemotherapy.
- Newly diagnosed patients who do not start with treatment.
- Patients who started a previous MDS related treatment less then 4 weeks ago.
- Patients who started a previous MDS related treatment less then 12 weeks ago apart from packed cell transfusions.
- Diagnosis of any previous or concomitant malignancy **except** when the patient successfully completed treatment (chemotherapy and/or surgery and/or

radiotherapy) with curative intent for this malignancy at least 3 months prior to inclusion.

- Patients refusing to sign informed consent

8 Treatment scenarios

Possible different scenarios and what to do when any of those scenarios occur, are outlined in the flowchart 'Treatment scenarios'.

8.1 Standard study visits

The patient will fill out the QUALMS and B-IPQ at timepoints 0 (at timepoint new diagnosis or timepoint new therapy), at 4 weeks, at 12 weeks and at 24 weeks on treatment. The treating physician will fill out the corresponding CRF at each timepoint. Beyond 24 weeks, no follow-up is needed.

8.2 Treatment under investigation is stopped

In case the patient stops the previously started treatment that is currently under investigation before the evaluation at 24 weeks is done, an end of treatment evaluation and follow-up needs to be performed as outlined in the section beneath 'follow-up'.

8.3 A new treatment is added less then 4 weeks after starting the investigational treatment

In case another therapy is added within 4 weeks of a previously started treatment, the patient drops out of the study. This needs to be reported to the coordinating center. No further follow-up is needed. The patient can be included in this study in the future in case the in- and exclusion criteria are met.

8.4 A new treatment is added between the timepoint of 4 and 12 weeks

If the previous treatment under investigation is transfusion of packed cells, the patient can continue to participate in this study and will restart at time point 0. The patient will cross over to the other treatment cohort. Further timepoints will be as outlined previously with completion of the questionnaires at 4, 12 and 24 weeks after the start of this new therapy.

In case the previous treatment is any other therapy than transfusion of packed cells the patient will drop out of the study. This needs to be reported to the coordinating center. No further follow-up is needed.

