8.10 The patient dies during the study period

In case the patient dies during the study, the cause of death needs to be reported to the coordinating center.

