8.13 Sequential inclusion of the same patient

In case the patient meets inclusion and exclusion criteria at a later stage, participation is allowed after filling out the application form. The same unique patient code will always be used for the same patient,

even when he drops out of the study and is included again afterwards. When included again the patient will always start at timepoint 0.

Figure 1: Flowchart Treatment Scenarios

9 Treatments studied

As mentioned before, treatment options in regard to MDS are limited for the moment. In this study, we aim to evaluate 7 treatment groups. Patients included in an interventional trial with a treatment not included in one of the 7 groups can be included but will not be part of the statistical analyses. However, the data of those patients will be reported. Specific side effects of the different treatments need to be reported as mentioned in the study safety paragraph. The different treatment groups are:

9.1 Packed cells transfusions without other treatments.

This group contains patients receiving packed cell transfusions at a rate that is determined by the treating hematologist and at a hemoglobin threshold or with a hemoglobin goal determined by the treating hematologist. In this group only patients will be evaluated who did not receive any transfusions in the past in regard to their diagnosis of MDS. The first QUALMS can be filled out during the first transfusion. In case transfusion is urgent, the first QUALMS can be filled out until 2 weeks after the first transfusion. In this case the patient must be asked to fill out the questionnaires as he was before the first transfusion. Beyond two weeks of the first transfusion we do not consider the patient to be able to recall their situation precise enough to fill out the questionnaires in retrospect. When the questionnaires are filled out in retrospect, the date of first transfusion will be taken as time point 0. The next measuring point is 4 weeks after the first transfusion as mentioned earlier. Since transfusion instantly contributes to a better hemoglobin value, we expect to measure an immediate impact on QOL.

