9.7 Intensive chemotherapy

This therapy is frequently used to reduce disease burden in anticipation to allogeneic stem cell transplantation. Without stem cell transplantation, a durable remission can be obtained but will bring no cure. Different regimens can be used. Intensive chemotherapy is considered to be high dose chemotherapy that is administrated intravenously in the hospitalized patient resulting in a prolonged period of neutropenia. No difference will be made between different regimens that are used. Since this treatment comes with his own peculiar physical and psychological impact other treatments may be started at the same moment. If the patient is treated with intensive chemotherapy he will be evaluated in the intensive chemotherapy-group only from the moment he starts this treatment.

10 Study procedures

Patients will be asked to fill out the QUALMS and the B-IPQ before starting treatment or before the start of a new therapy. The first visit, patients fill out the QUALMS and B-IPQ will be between 2 weeks before starting this therapy and the actual moment of their new treatment.

Repeated testing using the QUALMS and B-IPQ will be done 4, 12 and 24 weeks after the actual start of therapy. The treating hematologist will be asked to fill out a case report form (CRF), every time the QUALMS and B-IPQ are filled out by the patient. All questionnaires must be filled out on site only. It is not allowed to take the questionnaires home. The first QUALMS and B-IPQ must be filled out in the ambulatory setting.

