11.1 Withdrawal of individual patients from protocol treatment

Patients should be withdrawn from protocol if any of the following criteria for withdrawal are met:

- ◆ Death
- ◆ Patient receiving different treatments within a timespan that is not allowed according to this protocol as mentioned earlier
- ◆ Patients developing another malignancy
- ◆ Patients progressing to acute leukemia
- ◆ Patients proceeding to allogeneic stem cell transplantation

Patients are allowed to withdraw from the study at any time for any reason if they wish to do so without any consequences. The investigator can also decide to withdraw a patient from protocol for other reasons than the criteria described above.

12 Safety

12.1 Reporting of adverse events.

An adverse event (AE) is any unfavourable and unintended sign (including an abnormal laboratory finding), symptom, or disease temporally associated with the use of a medical treatment or procedure that may or may not be considered related to the medical treatment or procedure. In contrast, an adverse reaction is characterized by the causal relationship between a medicinal product and any negative occurrence. The Belgian law recommends all physicians to report adverse reactions to the federal agency for medicines and health products (famhp) by use of the yellow paper or online.

Due to the purely non-interventional nature of this study, reporting to the sponsor should be done as per legislation for spontaneous reporting. In case an adverse reaction occurs, a parallel reporting to the famph and to the coordinating centre of this study must be performed. The coordinating centre (sponsor) will forward this report to Celgene. A general understanding to any occurred adverse events in the preceding period will come forward in the CRF that will be filled out during follow-up as outlined previously.

In case pregnancy occurs during study while the patient is taking an 'imid' drug, the drug must be stopped immediately and reporting should be done by the local investigator in accordance with the obligatory pregnancy prevention program (PPP) before prescribing an 'imid' drug.

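### Patients who drop out because a therapy is added (before week 4, or at weeks 4-12 on a treatment other than packed cells) have no exit QUALMS, B-IPQ or CRF, unlike the other non-fatal exits in section 8

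*Combined protocol and SAP*

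**What the plan says.** Section 8.3 covers an addition in the first four weeks: "In case another therapy is added within 4 weeks of a previously started treatment, the patient drops out of the study". The drop-out is notified to the coordinating centre and follow-up ends. Later re-entry is possible: "The patient can be included in this study in the future in case the in- and exclusion criteria are met".

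Section 8.4 covers weeks 4 to 12 and has two branches. The first keeps the patient, with a return to timepoint 0: "If the previous treatment under investigation is transfusion of packed cells, the patient can continue to participate in this study and will restart at time" (quote cut short here). The second does not: "In case the previous treatment is any other therapy than transfusion of packed cells the patient will drop out of the study". Here too the drop-out is notified and follow-up ends.

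On forms, section 10 asks the haematologist to "fill out a case report form (CRF), every time the QUALMS and B-IPQ are filled out by the patient". On adverse events, 12.1 says: "A general understanding to any occurred adverse events in the preceding period will come forward in the CRF". Separately, 12.1 requires adverse reactions to be reported in parallel to the national agency and the coordinating centre. Section 9 adds: "Specific side effects of the different treatments need to be reported as mentioned in the study safety paragraph".

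**The concern.** A patient who stops a drug at week 3 completes an end-of-treatment evaluation and a follow-up four weeks later. A patient who has a second drug added at week 3 provides nothing after baseline. Needing an addition this early may mean that the first treatment was not working or was poorly tolerated, so the loss may be related to the outcome.

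Two things are at stake. The primary endpoint is the change in QUALMS at 4, 12 and 24 weeks. If patients with early additions fare differently, the estimated early change describes mainly those who needed no addition, and there are no data to check this. In addition, because the CRF is tied to questionnaire completion, no questionnaire at exit means no CRF, so general adverse events since the last visit go uncollected for these patients.

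**Working it through.** **1. The section 8 scenarios side by side**

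| Section | Event | Patient then | Exit QUALMS, B-IPQ and CRF |
|---|---|---|---|
| 8.2, 8.11 | Treatment stopped before week 24 | Leaves, after a follow-up | Required |
| 8.3 | Therapy added before week 4 | Leaves | None specified |
| 8.4, first paragraph | Added at weeks 4-12, on packed cells | Restarts at timepoint 0 | New baseline set instead |
| 8.4, second paragraph | Added at weeks 4-12, on anything else | Leaves | None specified |
| 8.5 | Added after week 12 | Restarts at timepoint 0 | New baseline set instead |
| 8.6 | Stopped and switched at once | Restarts | Required; serves as first timepoint |
| 8.7 | Allogeneic transplant | Leaves | Required |
| 8.8 | Acute leukemia | Leaves (11.1), after a follow-up | Required |
| 8.9 | Another malignancy | Leaves | Required |

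Only 8.3 and the second branch of 8.4 leave no record around the event.

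**2. Can another rule supply the record?** Section 8.11 triggers the evaluation when treatment is stopped, and an addition is not a stop. Dropping out does not explain the omission: 8.9 combines drop-out with an evaluation, and 8.7 combines an evaluation with no later follow-up. Re-entry does not recover the observation: 8.13 starts a re-included patient at a new timepoint 0, and the exclusions in 7.1.2 on recently started treatment apply first.

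**3. What is lost.** CRFs are due at weeks 0, 4, 12 and 24 (8.1).
- 8.3: the last CRF is at week 0. Up to 4 weeks of CRF adverse events are lost, and there are 0 post-baseline QUALMS scores.
- 8.4, second branch: the last CRF is normally at week 4. Up to 12 - 4 = 8 weeks are lost; the week-4 score stands.

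**4. The plan's own drop-out allowance (14.2).** The inputs are a 7.5-point difference, an SD of 15 (used as the SD of the paired difference), two-sided alpha 0.016 and 80% power. A paired t-test with effect size 7.5/15 = 0.5 gives n = 45.20, and 45.20 x 1.10 = 49.72, rounded to 50. The plan's figure reproduces. With 50 enrolled, 10% loss leaves 45 and 79.8% power; assumed losses of 20% and 30% leave 40 and 35, with 73.7% and 66.4%. The allowance covers the number lost. It does not address which patients are lost.

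**5. Possible bias, with assumed values only.** Let p be the share with an early addition, R the mean change in retained patients and A the mean change in the others. The true mean is (1 - p)R + pA. If only retained patients inform the change, the error is R - [(1 - p)R + pA] = p(R - A).

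| p (of 50) | R - A = 0 | R - A = 7.5 | R - A = 12.5 (R = +5, A = -7.5) |
|---|---|---|---|
| 10% (5) | 0 | 0.75 | 1.25 (true +3.75, seen as +5) |
| 20% (10) | 0 | 1.5 | 2.5 (true +2.5, seen as +5) |

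The sign reverses if A exceeds R. The formula fits 8.3 patients with baseline scores like those of the rest. For 8.4 patients it overstates the problem, because their week-4 score enters the mixed model.

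**The case against.** The contrast has a logic. Section 8.11 links the evaluation to stopping treatment, and a patient who adds a therapy has not stopped. Failure that leads to a stop or a switch is already recorded under 8.2 and 8.6. This explains how the gap arose but does not close it.

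A reader might infer that everyone who adds a therapy before week 12 leaves. The documents do not support that: packed-cell patients at weeks 4-12 stay and start a new series.

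A reader might also infer that adverse events in these patients are never recorded. That is too strong. Section 12.1 requires adverse reactions to be reported whichever study form is due, and CRFs already completed stand. The section 9 sentence on side effects points to that same safety paragraph, so it is not breached. Safety is neither an objective nor an endpoint. What remains is the loss of general adverse events that only the CRF collects, since the last visit.

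A third tempting reading is that early treatment failure is missed and the primary result is biased. An addition is only a possible sign of failure; the treatments studied include transfusion and iron chelation, so an added therapy may be supportive. No rate of early additions is given.

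One further objection stands in full. The model in 14.3 treats time as categorical and compares weeks 4, 12 and 24 with baseline. A score taken at week 2 or week 9 has no place in it unless a use is stated, so collection alone would not repair any bias.

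**Conclusion.** The gap is real but limited. In 8.3 and the second paragraph of 8.4, no exit questionnaire or CRF is specified, although the other non-fatal exits in section 8 have one. The loss is the quality-of-life score at the addition plus up to 4 weeks (8.3) or 8 weeks (8.4) of CRF-collected adverse events. Patients under 8.3 contribute a baseline only, so they give no direct information on change. The size of any bias is unknown: the 0 to 2.5 points shown rest on assumed rates and differences, and only illustrate what would matter against the 7.5-point target.

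This is a cheap improvement, worth making because the data cannot be recovered later by analysis. It does not invalidate the design or the sample size. A reader might extend the point to deaths, where 8.10 says only that "the cause of death needs to be reported to the coordinating center"; that is a separate and minor matter, since no patient questionnaire is possible.

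Two limits apply. The flowchart in Figure 1 could not be read, and the further statistical analysis plan to which 14.3 refers is not in the text available. If either already provides for these exits, the written sections need only be reconciled with it.

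**What to change.** In 8.3 and in the second paragraph of 8.4, replace the sentence that waives further follow-up with wording such as: *The existing end-of-treatment evaluation (QUALMS, B-IPQ and end-of-treatment CRF) is completed at the visit where the therapy is added. The CRF records whether the questionnaires were completed before or after the added therapy started. After this, the patient has no follow-up.* Widen the trigger in 8.11 to match, and align Figure 1 if needed.

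In 14.3 or the statistical analysis plan, state that these exit scores will be described by treatment group and used in a sensitivity analysis of the change at the next scheduled timepoint (week 4 for 8.3, week 12 for 8.4). Report the number of such exits per group.

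The drop-out rule, treatment decisions and sample size do not change. The cost is a short amendment and one existing form set per affected patient. Section 10 requires completion on site, so some evaluations may be missed or completed after an urgent start; the before/after item makes that visible.
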